2.1. Objectives

The objective of this clinical study is to evaluate the safety and effectiveness of the Ellipse VR/DR implantable cardiac defibrillators (ICDs) and the Quadra Assura MP cardiac resynchronization therapy defibrillators (CRT-Ds), with Durata or Optisure defibrillation leads, Tendril STS or Isoflex pacing leads, and the Quartet quadripolar leads in a 1.5T MRI environment for MR-conditional labeling expansion of these market-approved ICD/CRT-D systems in China.

There are four device combination groups in this clinical study as outlined below:

- **Group 1:** Ellipse VR single-chamber ICD with a Durata lead in the right ventricle (RV).
- **Group 2:** Ellipse DR dual-chamber ICD, with a Durata lead in the RV and a Tendril STS lead in the right atrium (RA).
- **Group 3:** Ellipse DR dual-chamber ICD with a Optisure lead in the RV and a Isoflex lead in the RA.
- **Group 4:** Quadra Assura MP CRT-D with a Durata or Optisure lead in the RV, a Tendril STS or Isoflex lead in the RA, and a Quartet lead in the left ventricle (LV).

FIGURE 1: STUDY GROUP OVERVIEW

2.2. Primary Endpoints

- Safety: Freedom from MRI-scan related complications related to the ICD/ CRT-D device and/or leads from the time of the MRI scan to 1-month post-MRI scan testing.
- Effectiveness: Proportion of leads with a capture threshold increase of $\leq 0.5V$ at 0.5ms for RA and RV leads and $\leq 1.0V$ at 0.5ms for LV leads from pre-MRI scan to 1-month post-MRI scan testing.
- Effectiveness: Proportion of leads with a sensing amplitude decrease of $\leq 50\%$ from pre-MRI scan testing to 1-month post-MRI scan.

2.3. Descriptive Endpoint(s)

Descriptive endpoints are reported using only summary statistics and no hypothesis tests will be performed.

The following data will be collected:

1. Demographics: gender, age, ethnicity, race, cardiac disease history, arrhythmia history, indication for ICD/CRT-D implant, history of smoking, etc.
2. Device electrical measurements at the MRI Scan Visit (pre- and post-scan) and at the 1 Month Post Scan Visit
3. ADE, SADE, USADE
4. Mortality
5. Number of non-study MRI scans
6. Summarize number of subjects that returned to usual programming after the MRI scan and number of subjects, if any, experiencing delays in reprogramming

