Baseline/ MRI Scan Visit	
45 (+7) days after implantation or after most recent lead revision
 
MRI scan should occur within 14 days of Baseline visit.
 
The pre-MRI scan, MRI, and post MRI scan procedures should occur on the same day.
	
Pre-MRI Scan testing
 
 Assess inclusion/exclusion criteria Screen, clear and prep subject for MRI scan Complete MRI screening form Complete MRI Hazard Checklist Administer pregnancy test – can be done up to 7 days before MRI scan Interrogate device Perform capacitor maintenance Obtain in-clinic lead measurements: bipolar capture, sense, pacing and HVLI impedances^{1,2} Setup and activate MRI Settings 
During MRI Scan
 
 Monitor subject with ECG, or pulse oximetry, and verbal communication 
Post-MRI scan testing
 
 Interrogate device Deactivate MRI Settings Obtain in-clinic lead measurements: bipolar capture, sense, pacing and HVLI impedances^{1,2} Evaluate subject for any adverse events (serious and non-serious) and submit an AE CRF (as applicable). Report deviations, screening failure/withdrawal and out of service as applicable Submit MRI scan results, e.g. scan time, sequences used, etc. Upload device session records through the EDC study site portal
1-Month Post MRI Scan Visit	30 days after MRI scan (0/+14 days)	
 Interrogate device Obtain in-clinic lead measurements: bipolar capture, sense, pacing and HVLI impedances^{1,2}

Study Visit	Visit Window	Study Procedures and Data Collection
		
 Evaluate subject for any adverse events and submit an AE CRF (as applicable). Report deviations, withdrawal and out of service as applicable Upload device session records through the EDC study site portal
System Revision (if applicable)	Can occur any time after implant	
 Interrogate device Obtain applicable in-clinic lead measurements: bipolar capture¹, sense², and pacing and HVLI impedances for cases where the lead was repositioned, or was replaced with another Durata/Optisure or Tendril/Isoflex, Quartet lead, or where the ICD/ CRT-D was replaced with another Ellipse ICD/ Quadra Assura MP CRT-D. Evaluate subject for any adverse events and submit an AE CRF (as applicable). Report deviations, withdrawal and out of service as applicable Upload device session records through the EDC study site portal

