
 • Refer to the Durata, Optisure, Tendril STS, Isoflex, and Quartet lead user's manual for a full list of potential adverse events 	
The Durata, Optisure, Tendril STS, Isoflex, and Quartet leads are market released transvenous, steroid-eluting

Event	Mitigation
	
leads. The adverse events associated with these leads are the same as those associated with other market-released transvenous leads.
 
These risks are mitigated through the selection of investigators who are qualified by training and/or experience to evaluate and treat subjects implanted with an ICD/ CRT-D system.

In addition, subjects may also experience unavoidable events related to the MRI scan. An unavoidable event is an event related to the MRI scan that is expected to occur for a projected duration in all subjects. Unavoidable events are not reportable unless the condition worsens or continues beyond the time frame listed below. Unavoidable events do not need to be reported on an adverse event form if they are resolved within the time frame specified. These events are expected to occur with any MRI scan, including the study MRI scans.

TABLE 11: UNAVOIDABLE EVENTS RELATED TO THE MRI SCAN

Event	Time Frame post – MRI scan
• Claustrophobia	• During MRI scan
• Mild diaphoresis	• During and < 1-hour post MRI scan
• Sensation of bodily warmth	• During and < 1-hour post MRI scan
• Sensation of warmth at device pocket not arising to the level of discomfort	• During and < 1-hour post MRI scan
• Hearing impairment	• < 24 hours
• Body stiffness related to immobility	• < 48 hours

SAE Reporting

The investigator should report all SAEs occurring after MRI settings have been programmed at the MRI study visit to the Sponsor as soon as possible but no later than outlined below.

Clinical Site	Reporting timelines
All Sites	SAEs should be reported to regulatory authorities and the Sponsor no later than 24 hours from the day the site personnel became aware of the event or as per the investigative site's local requirements, if the requirement is more stringent than those outlined.

The date the site staff became aware the event met the criteria of an SAE must be recorded in the source document. The Investigator will further report the SAE to the local IRB/EC according to the institution's IRB/EC reporting requirements.

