Appendix A: Definitions

Non-study Specific Definitions

Adverse Event (AE)

Any untoward medical occurrence, unintended disease or injury, or untoward clinical signs (including abnormal laboratory findings) in subjects, users or other persons, whether or not related to the investigational medical device under clinical investigation.

Note 1: This definition includes events related to the medical device under investigation or the comparator.

Note 2: This definition includes events related to the procedures involved.

Note 3: For users or other persons, this definition is restricted to events related to medical devices under investigation

Serious Adverse Event (SAE)

If the AE meets any of the criteria below, it is regarded as a serious adverse event (SAE).

- a) Led to a death,
- b) Led to a serious deterioration in health of the subject, that either resulted in
 1. a life-threatening illness or injury, or
 2. a permanent impairment of a body structure or a body function, or
 3. in-patient hospitalization or prolongation of existing hospitalization, or
 4. medical or surgical intervention to prevent life threatening illness or injury or permanent impairment to a body structure or a body function.
 5. chronic disease
- c) Led to fetal distress, fetal death or a congenital abnormality or birth defect.

Note: A planned hospitalization for pre-existing condition, or a procedure required by the CIP, without a serious deterioration in health, is not considered to be an SAE.

Adverse Device Effect (ADE)

An adverse event related to the use of an investigational medical device.

This definition includes adverse events resulting from insufficient or inadequate instructions for use, deployment, implantation, installation, or operation, or any malfunction of the investigational medical device.

This definition includes any event resulting from the use error or from intentional misuse of the investigational medical device.

Serious Adverse Device Effect (SADE)

Adverse device effect that has resulted in any of the consequences characteristic of a serious adverse event.

Unanticipated Adverse Device Effect (UADE)

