3.2 Adverse Events

CEC adjudicated ADE, SADE, USADE data will be summarized in terms of the number of events, the number of subjects with event(s), and the percentage of subjects with event(s). Subjects who die or withdraw before 1-month post-MRI scan will be included in the denominator, and their last known status of event will be included in the numerator.

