3.5 Descriptive Endpoints or Additional Data

Following Descriptive Endpoints will be reported using only summary statistics and no hypothesis tests will be performed.

- 1) Demographics: gender, age, ethnicity, race, cardiac disease history, arrhythmia history, indication for ICD/CRT-D implant, history of smoking, etc. Refer to Section 3.1 for the detail.
- 2) Device electrical measurements: device electrical measurements at the MRI Scan Visit (pre- and post-scan) and at the 1-Month Post Scan Visit will be summarized based on Analysis Cohort subjects who undergo the 1-month post-MRI scan testing, and with evaluable device data available for analysis to be performed.
- 3) ADE, SADE, USADE: Refer to Section 3.2 for the detail.
- 4) Mortality: The number of subjects who die and the primary cause of death will be presented based on the CEC adjudicated data.
- 5) Non-study MRI scan data: The number, type, available adverse event(s), and key electrical measurements will be summarized for non-study MRI scans performed.
- 6) Summarize number of subjects that returned to usual programming after the MRI scan and number of subjects, if any, experiencing delays in reprogramming: Data will be summarized descriptively based on available information from MRI Scan form. A subject with 'Yes' to question of 'Were the MRI settings disabled after MRI scan' in MRI Scan form is considered as 'returned to usual programming after the MRI scan'.

In addition, the adverse events and mortality that are reported prior to the completion of the study pre-MRI scan visit on the All Consented subjects will be summarized separately using descriptive statistics. Listings of the adverse events and mortality with an event description will be provided as appropriate.

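### Non-fatal SAEs after MRI programming that are judged not device-related are reportable under the CIP's SAE rule but appear in no planned table

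*Combined protocol and SAP*

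**What the plan says.** **What is tabulated.** Item 3 of the descriptive endpoints in CIP 2.3, repeated in SAP 1.4.3, reads "3. ADE, SADE, USADE". SAP 3.2 carries it out: "CEC adjudicated ADE, SADE, USADE data will be summarized in terms of the number of events", with subject counts and percentages. SAP 3.5 item 3 only refers back to 3.2. Appendix A defines an ADE as "An adverse event related to the use of an investigational medical device". A SADE is an ADE with a serious consequence, and a USADE is a SADE not foreseen in the risk analysis. All three therefore require device-relatedness. An adverse event, on which the SAE definition is built, counts "whether or not related to the investigational medical device under clinical investigation". Mortality is a separate item (item 4): SAP 3.5 presents all deaths with the adjudicated primary cause.

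**What is to be reported.** Under SAE Reporting in CIP 16.1.2: "The investigator should report all SAEs occurring after MRI settings have been programmed at the MRI study visit to the Sponsor". There is no relatedness condition. Table 4 (CIP 8.4.4), for post-scan testing, says: "Evaluate subject for any adverse events (serious and non-serious) and submit an AE CRF (as applicable"; its 1-month entry also asks for any adverse events.

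**Narrower text on the same matter.** The list of reportable events in CIP 16.1.2 names ADEs and SADEs only. CIP 16.1.1 makes a class of unrelated events non-reportable, in wording that cannot be parsed with confidence. The 1-month visit (8.4.4.7.1 and 8.4.4.7.2) evaluates for ADEs and SADEs and ties the AE form to them. Unscheduled visits (8.4.8) are defined by an ADE or SADE.

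**The concern.** The study is open-label and single-arm, so whether a serious event after the scan is device-related is a judgement made without a comparison group. Appendix A gives that judgement first to the investigator. The planned tables then contain only events that passed it.

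The judgement is hard in this population. Table 10 lists VT/VF, hemodynamic collapse and pulmonary embolism among potential MRI-related events. CIP 4.2 describes the devices as treatment for life-threatening ventricular arrhythmias. A ventricular arrhythmia leading to hospital admission two weeks after the scan has two credible explanations. If it is attributed to underlying disease, it leaves every planned event table. The CEC would not necessarily correct this, because its stated scope (CIP 8.1.3 and 8.3.2) is device effects and deaths.

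At stake is whether a reader of the report can see the non-fatal serious events that followed the investigational exposure and judge the attribution independently.

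**Working it through.** The check compares what is reportable with what is tabulated, for serious events from MRI programming to the 1-month visit.

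| Serious event after MRI programming | Reportable? | Planned table |
|---|---|---|
| Non-fatal, device-related (SADE, USADE) | Yes, under the SAE rule and under the reportable-event list in CIP 16.1.2 | SAP 3.2; SAP 3.5 item 3 |
| Fatal, related or not | Yes (CIP 16.1.3) | SAP 3.5 item 4, with primary cause; also SAP 3.3 as early termination |
| Non-fatal, judged not device-related | Yes under SAE Reporting in 16.1.2 and Table 4; not named in the reportable-event list in 16.1.2, in 8.4.4.7 or in 8.4.8 | None |

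1. **Primary safety endpoint.** Appendix A defines a complication as a SADE that needs an invasive intervention or leads to death, and the endpoint further requires it to be MRI-related. It is narrower than the first two rows and cannot pick up the third.
2. **Rest of the SAP.** In the visible text, SAE occurs only in the abbreviation list. A withdrawal prompted by such an event would be counted under SAP 3.3 as a withdrawal, not as an SAE.
3. **Adjudication.** An event the investigator calls unrelated is not an ADE, so it falls outside the CEC's stated scope unless the CEC charter, which is not among the documents, adds it. Even if the CEC reviews the event and agrees that it is unrelated, SAP 3.2 still leaves it out.
4. **Is relatedness available for a split?** Appendix A has the investigator's device-relationship assessment recorded on the CRF, and CIP 18 requires source documentation of it for SAEs.
5. **Redaction.** Parts of SAP 2.1, 2.3.1, 2.3.2 and 3.4 are blacked out. SAP 3.2 and 3.5, where an SAE table would sit, show no redaction. A table hidden elsewhere is unlikely but cannot be excluded.

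**Size of one omitted event.** CIP 8.1.12 enrols 15 per group to retain at least 10, allowing for attrition of 5.

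- Nobody lost before programming: 1/15 = 6.7% of the group.
- All 5 lost before programming: 1/10 = 10% of the group.

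The documents give no SAE rate, so the expected number of omitted events is not calculated.

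**The case against.** The other side has several good points.

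- **Deaths are covered.** A reader might infer that no serious event judged unrelated is tabulated. That is wrong for fatal events: mortality is the next item in the list and has no relatedness filter. The gap is confined to non-fatal events.
- **Other results do not depend on attribution.** A reader might infer that an all-cause SAE count would be the only such safety result. All-cause mortality is planned, and the lead electrical measurements need no causality judgement.
- **Collection is contested.** The narrower reporting text means complete SAE data on the AE CRF cannot be assumed. A table built without first settling this could present a partial count as complete. This stands, and it belongs in the fix.
- **The pre-scan and non-study-scan contrast is weak.** SAP 3.5 summarises "the adverse events and mortality that are reported prior to the completion of the study pre-MRI scan visit on the All Consented subjects", and for non-study scans it summarises available adverse events. A reader might infer that the study-scan window gets the narrowest class. But CIP 16.1.1 makes events before programming non-reportable to the sponsor and routes them through complaints, so few may be there to summarise. For non-study scans CIP 8.4.10 collects adverse device effects. The contrast rests on loose wording, and an added table would not make the periods comparable.
- **The number affected is unknown.** A reader might apply an assumed SAE rate to all 60 subjects. That would count device-related and fatal events that are tabulated, and subjects never programmed for MRI. If the allowed attrition all came first, 4 x 10 = 40 subjects would remain.
- **Oversight and reporting exist.** SAEs go to the sponsor and the authorities within 24 hours and to other institutions and ethics committees (CIP 16.1), and CIP 20 has a general adverse-event heading in each report. These events are therefore not hidden. A report heading is still not a specified analysis.
- **No endpoint is affected.** The study is descriptive with no success criterion (SAP 2.2, 2.7). This limits the weight of the point but does not remove it.

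**Conclusion.** The point holds for one class: non-fatal SAEs after MRI programming that are judged not device-related. The SAE rule and Table 4 bring them in; CIP 2.3 and SAP 1.4.3, 3.2 and 3.5 leave them out of every planned table. They may also go unadjudicated. One such event is 6.7% to 10% of a device group, depending on how many of the 15 enrolled reach programming.

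The conclusion assumes that the redacted SAP text holds no SAE table and, for adjudication only, that the CEC charter does not widen the stated scope. It does not rest on any SAE rate. It changes no endpoint or success criterion. It is a reporting gap that is cheap to close in a study meant to support scan safety.

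**What to change.** 1. **Reconcile the reporting text.** Bring CIP 8.4.4.7.1, 8.4.4.7.2, 8.4.8, 16.1.1 and the reportable-event list in 16.1.2 into line with the SAE Reporting text and Table 4. It should be clear that all SAEs from MRI programming to the 1-month visit are recorded on the AE CRF, whatever the judged relatedness. Rewrite the unclear exclusion in 16.1.1.
2. **Add one table and one listing.** In CIP 2.3 item 3 and SAP 1.4.3, 3.2 and 3.5, add all SAEs in that window: events, subjects, and percentage of subjects whose MRI settings were programmed, overall and per group. Split by investigator relatedness, and by CEC relatedness where adjudicated. Keep subjects who die or withdraw in the denominator, as SAP 3.2 already does. Leave the ADE, SADE and USADE tables unchanged.

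**Cost.** One more table and listing, short text changes in the CIP and SAP, and possibly a few more AE CRFs at sites that followed the narrower list. No visits or procedures change.

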2.4. Contents

This document is a clinical investigation plan (CIP) for the observational clinical study of the safety and effectiveness of the Ellipse VR/DR implantable cardiac defibrillators (ICDs) and the Quadra Assura MP cardiac resynchronization therapy- Defibrillators (CRT-Ds), with Durata or Optisure defibrillation leads, Tendril STS or Isoflex pacing leads, and the Quartet quadripolar lead in a 1.5T MRI environment in China. This clinical study is intended to support MR conditional labeling expansion approval from the China National Medical Products Administration (NMPA) for these market approved ICD/CRT-D systems in China. This clinical study is sponsored by Abbott.

This clinical study will be conducted in accordance with this CIP. All investigators involved in the conduct of the clinical study will be qualified by education, training, or experience to perform their tasks and this training will be documented appropriately.

3. Background information of the clinical study

Magnetic resonance imaging (MRI) is a non-invasive imaging technique capable of providing high-quality images of the whole human body. MRI can provide images of excellent spatial resolution together with functional and tissue characterization information without the use of damaging ionizing radiation and potentially nephrotoxic iodinated contrast agents in two and three dimensions.¹ For these reasons, MRI is the imaging modality of choice in a wide spectrum of diseases, not only for diagnosis but also for staging and follow-up of affected patients, including those with involvement of the neurological, musculoskeletal, oncological, and cardiovascular systems. This has led to a recent rapid increase of the number of MRI scans performed.² In 2007, an estimated 27.5 million MRI procedures were performed in the U.S. in 7,195 hospital and non-hospital sites.³

According to the 2009 World Survey of cardiac pacing and cardioverter defibrillators, 235,567 new pacemakers were implanted in the United States in 2009. When compared to a similar survey conducted in 2005, the 2009 survey showed an increase in the number of pacemakers and defibrillators implanted throughout the world, a trend that is likely to continue.^{4,5} It is estimated that 50-75% of patients with implantable cardiac devices will develop an indication for an MRI scan during the lifetime of their device.⁶

Magnetic resonance imaging systems generate three electromagnetic fields that are used to produce an image. These include a static magnetic field, a time varying gradient magnetic field, and an RF field. All three of these fields interact with implanted devices and could create hazards for the device, the patient, or both. Examples of these hazards include unwanted cardiac stimulation, heating near lead electrodes, image artifacts, and forces being applied to implanted components.^{7,8} Due to these issues, certain currently marketed implantable cardiac device systems, including ICDs and CRT-Ds, may be contraindicated for use in an MRI environment. There is a specific need for device manufacturers to give clinical evidence that MR conditional systems provide evidence of patient safety who receive MRI scans.⁹

Over the past 10 years, there have been numerous patients with implanted devices who successfully underwent magnetic resonance imaging.^{10,11,12,13,14,15}

In this study, Abbott plans to evaluate the safety and effectiveness of the Ellipse VR/DR, ICDs, the Quadra Assura MP CRT-Ds, with Durata or Optisure defibrillation leads, Tendril STS or Isoflex pacing leads, and the Quartet quadripolar left heart lead in a 1.5T MRI environment for MR-conditional labeling expansion of these market-approved ICD systems in China.

4. Features of product, structure and composition, operating principle, mechanism of action and scope of study

